1. STUDY SUMMARY

Title	Home Telemonitoring In Patients after Myocardial Infarction Experience, HELP ME trial.
Methodology	
Randomized, parallel-group clinical trial in acute coronary syndrome patients which have undergone coronary angiography with two study groups:
 
Group 1: Discharged home with standard medical treatment.
 
Group 2: Discharged home with standard medical treatment and 12 lead ECG telemonitoring device for 90 days.

Overall Study Duration	2 years
Subject Participation Duration	90 days
Single or Multi-Site	Single Site Mayo Clinic Rochester, MN
Objectives	
Several retrospective studies indicate that patients with ACS post PCI have less readmissions and better survival with 12 lead ECG telemonitoring at home. So far, no prospective study was done to show this benefit.
 
The objective of the current study is to evaluate the incidence of ED visits, re-hospitalizations and major adverse cardiovascular events (MACE including cardiovascular death and hospitalization for myocardial infarction, unstable angina, repeat revascularization, heart failure, stroke, arrhythmias, and cardiac arrest), and cost-effectiveness over a period of 90 (+/- 7) days after an index hospitalization for an acute myocardial infarction (MI).
 
Our central hypothesis is that 12 lead ECG home telemonitoring decreases general and cardiac ED presentation and hospital readmission rates without an increase in MACE and at a lower health care utilization cost compared to patients with standard therapy alone.
 
Three specific aims will be pursued:
 
Aim 1: To compare the rates of ED visits and re-hospitalization rates as well as related downstream cardiovascular testing (echocardiogram, stress test or coronary CT, or invasive coronary angiogram) from discharge after index hospitalization for MI to 90 days follow-up between patients undergoing standard care alone or standard care plus the home 12 lead ECG telemonitoring device
 
Aim 2: To compare the rates of MACE from discharge after index hospitalization for MI to 90 days follow-up between patients undergoing standard care alone or standard care plus the home 12 lead ECG telemonitoring device
 
Aim 3: To compare health care cost utilization from discharge after index hospitalization for MI to 90 (+/-7) days follow-up between patients undergoing standard care alone or standard care plus the home 12 lead ECG telemonitoring device

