3.2 Secondary Objectives

The secondary objectives of this study are:

- a) To compare the rates of cardiovascular and non-cardiovascular ED visits and re-hospitalizations rates, from discharge after index hospitalization for MI to 90 (+/-7) days follow-up between patients undergoing standard care alone or standard care plus the 12 lead ECG Smartheart home telemonitoring device.
- b) To compare the rates of downstream cardiovascular testing (echocardiogram, stress test or coronary CT, or invasive coronary angiogram) from discharge after index hospitalization for MI to 90 (+/-7) days follow-up between patients undergoing standard care alone or standard care plus the 12 lead ECG Smartheart home telemonitoring device.
- c) To compare the rates of MACE from discharge after index hospitalization for MI 90 (+/-7) days follow-up between patients undergoing standard care alone or standard care plus the 12 lead ECG Smartheart home telemonitoring device.
- d) To compare health care cost utilization (including all cardiovascular inpatient and outpatient office visits and tests) from discharge after index hospitalization for MI to 90 (+/-7) days follow-up between patients undergoing standard care alone or standard care plus the 12 lead ECG telemonitoring device.
- e) To compare quality of life (MacNew Heart Disease Questionnaire) from discharge after index hospitalization for MI to 90 (+/-7) days follow-up between patients undergoing standard care alone or standard care plus the 12 lead ECG telemonitoring device.

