9. STATISTICAL CONSIDERATIONS

9.1. General Design Issues

This study will be conducted as a parallel group randomized clinical trial. The main goal is to define if Smartheart 12 lead ECG home device will decrease the rates of ED visits and rehospitalization in patients after index hospitalization for acute MI.

Our central primary hypothesis is that the Smartheart 12 lead ECG home device will decrease the ED visits and rehospitalization rates, leading to subsequent decrease in healthcare costs. Additional potential benefit is decrease in mortality by identifying any cardiac emergency at the early stage with appropriate urgent medical assistance. The quality of life of patients with the Smartheart device at home could be improved, knowing there is an easily available tool which can provide quick and reliable diagnosis.

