9.2. Sample Size and Randomization

Patients will be randomized to either standard medical therapy or the medical therapy plus the Smartheart 12 lead ECG home device.

The primary combined endpoint parameter is the rate of ED visits/rehospitalizations as well as related downstream cardiovascular testing (echocardiogram, stress test or coronary CT, or invasive coronary angiogram) at 90 (+/-7) days after discharge and mortality rates during the 90 (+/-7) days of follow up. Based on the most recent in-house registry data, we have about 50 AMI patients undergoing PCI a month. Accordingly, we have at least 600 patients a year who are discharged with a diagnosis of AMI from Saint Mary's Hospital.

Our own registry data further indicate that 24% of revascularized AMI patients will present to the ED or will be readmitted within 90 days. This is in keeping with the published literature citing a rate of 20-30%. Half of these patients will present for cardiovascular complaints and may get further testing, including echocardiogram, stress test or coronary CT, or invasive coronary angiogram. Having a 12-lead ECG available and the phone triage available to direct care may impact not only emergency presentation but also downstream testing. This will be considered in this trial, and each of these will be considered as a component to the combined primary endpoint event. Assuming that patients presenting with cardiovascular concern may receive two of the outlined downstream test as they present to the ED and hospital, the estimated event rate will be 48%. With 120 patients in each arm the study we would be adequately powered (beta error <0.2) to show a statistically significant (at alpha error levels of <0.05) for a 37.5% event reduction.

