9.5.2.1. Outcome measures

- Rate of ED visit and rehospitalization, overall and related to cardiovascular and non-cardiovascular causes
- Rate of downstream testing modalities (echocardiogram, stress test or coronary CT, or invasive coronary angiogram)
- Rate of MACE as defined above
- Amount of money in US dollars that was spent for any medical service related to cardiovascular and non-cardiovascular diseases in both study groups.
- Quality of life questionnaire score in both study groups at the time of enrollment and at 90 days.

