9.6. Data Analyses

The primary analysis for Aim 1 (lead aim of the study) will be a comparison of the rates of the primary combined endpoint between group 1 and 2 via Chi square test for categorical data of independent samples. The test will be used for any other categorical data. For continuous data, an independent groups t-test or Wilcoxon as appropriate after testing distributional assumptions.

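### Section 9.6's single rule for continuous outcomes gives the day-0 MacNew score no stated role and would probably send cost to a rank test that does not estimate mean dollars

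*Combined protocol and SAP*

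**What the plan says.** Section 9.6 assigns the chi-square test to the primary endpoint and other categorical data. It then gives one rule for everything else: "For continuous data, an independent groups t-test or Wilcoxon as appropriate after testing distributional assumptions". No variable, covariate, effect measure or interval is named.

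Two secondary outcomes come under this rule.

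- **MacNew.** Section 9.5.2.1 lists "Quality of life questionnaire score in both study groups at the time of enrollment and at 90 days". The Schedule of Evaluations places the questionnaire at day 0 and day 90 and does not restrict it to the device arm. Section 3.2(e) compares quality of life from discharge to 90 days. No section defines a change score or an adjustment.
- **Cost.** The Study Summary hypothesizes that telemonitoring works "at a lower health care utilization cost compared to patients with standard therapy alone" and lists as an objective "cost-effectiveness over a period of 90 (+/- 7) days after an index hospitalization". Section 9.1 expects fewer ED visits and rehospitalizations, "leading to subsequent decrease in healthcare costs". Section 9.5.2.1 counts dollars "spent for any medical service related to cardiovascular and non-cardiovascular diseases in both study groups", whereas 3.2(d) reads "To compare health care cost utilization (including all cardiovascular inpatient and outpatient office visits and tests".

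**The concern.** For MacNew, the plan collects a baseline measure of the outcome and then leaves open whether it enters the comparison. Randomization makes the day-90 and the change-score comparisons both unbiased, but they differ in precision, and ANCOVA is at least as precise as either. Leaving the choice open also allows it to be made after the data are seen.

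For cost, a hypothesis about lower spending and a cost-effectiveness objective both need a difference in mean dollars per patient, because mean cost times number of patients is what the payer spends. A rank-sum test addresses whether costs in one arm tend to be lower than in the other. With skewed data that can be a different question, and the result does not come in dollars. What is at stake is whether Aim 3 ends with a number on the scale of its own hypothesis.

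**Working it through.** **The plan's own figure.** The only power statement concerns the primary endpoint: 120 per arm, 48% reduced by 37.5% to 30%, beta below 0.2 (section 9.2). With pooled variance and two-sided alpha 0.05 (sidedness is not stated):

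- (0.18√120 − 1.96√(2×0.39×0.61)) / √(0.48×0.52 + 0.30×0.70) = (1.972 − 1.352)/0.678 = 0.914, giving power 82.0%.

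This agrees with the plan. No power or sample size is stated for MacNew or cost.

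**MacNew.** Let r be the correlation between day-0 and day-90 scores (not in the documents; assumed), with equal SDs at the two times. Relative to the variance of the day-90 comparison, the change-score comparison has factor 2(1−r) and ANCOVA has 1−r². The ratio of ANCOVA to change score is (1−r²)/(2(1−r)). The detectable difference with 120 per arm and 80% power is (1.960+0.842)√(2×factor/120) SD, which is 0.362 SD for day-90 scores.

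| r | ANCOVA vs day-90 variance | ANCOVA vs change variance | Detectable difference, ANCOVA | Power at 0.3 SD: day-90 → ANCOVA |
|---|---|---|---|---|
| 0.3 | 0.91 (9% lower) | 0.65 (35% lower) | 0.345 SD | 64% → 68% |
| 0.5 | 0.75 (25% lower) | 0.75 (25% lower) | 0.313 SD | 64% → 77% |
| 0.7 | 0.51 (49% lower) | 0.85 (15% lower) | 0.258 SD | 64% → 90% |

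Change scores are worse than day-90 scores at r = 0.3 (detectable difference 0.428 SD), equal at 0.5 and better at 0.7 (0.280 SD). The unspecified choice therefore matters.

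**Cost: which test the rule would select.** Section 9.2 puts 24% of patients in the ED or readmitted by 90 days, so 100 − 24 = 76% have neither. All dollar figures below are assumed: lognormal routine cost (median $1,000 to $5,000, log-SD 0.8) plus, for patients with an event, a lognormal event cost (median $15,000, log-SD 0.6, mean 15,000×exp(0.18) = $17,958). In these settings Shapiro-Wilk rejected normality in 100% of simulated control arms of 120.

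**Cost: do ranks track mean dollars?** Not necessarily. In a separate assumed model (zero cost for patients without an event, lognormal otherwise), mean cost was set equal in the two arms, with 24% of control and 15% of device patients having any cost. Wilcoxon rejected in 33% of trials and the Welch t-test in 5%. With equal medians but means of $4,915 and $9,182, Wilcoxon rejected in 5% and Welch in 58%.

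**Cost: power.** Percentage of simulated trials finding the device arm significantly cheaper, 120 per arm, ranges over the routine-cost medians:

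| Source of saving | True mean saving | Wilcoxon | Welch t |
|---|---|---|---|
| Fewer events, 24% vs 15% | 0.09×17,958 = $1,616 | 19–22% | 21–29% |
| All events 37.5% cheaper | 0.24×0.375×17,958 = $1,616 | 5–7% | 22–33% |
| Half of events 37.5% cheaper | 0.12×0.375×17,958 = $808 | about 4% | 8–10% |
| Routine cost 20% lower | 0.20×median×exp(0.32) = $275 to $1,377 | about 24–31% | about 4–17% |
| Fewer events, 48% vs 30% | 0.18×17,958 = $3,232 | 57–68% | 48–60% |

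The third row is the one closest to section 9.2 for savings on testing, which says "Half of these patients will present for cardiovascular complaints and may get further testing". Neither test dominates: means do better in the first three rows, ranks in the last two. The 37.5% is the plan's reduction in composite events, borrowed here as a cost reduction.

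**The case against.** Four counter-arguments deserve weight.

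- **The day-0 score is not excluded.** A reader might infer that the plan discards it. The documents do not support that: 9.5.2.1 names both time points, 3.2(e) runs from discharge to day 90, and 9.6 permits a t-test or Wilcoxon on change. This stands. What remains is that the role is unstated and no baseline adjustment is given. The precision gain depends on a correlation that the documents do not supply.
- **Wilcoxon is not a blunter tool here.** A reader might infer that ranks would miss savings that means would find. That holds if every event becomes cheaper, but section 9.2 ties further testing to only half of the presenting patients. With that half, both tests have little power, and if routine cost falls the ordering reverses. This stands, so power is no argument for means.
- **The plan does not forbid means.** The wording leaves room for a t-test, and nothing stops the report from giving mean dollars. True, but nothing commits to it either, and a literal distribution check points the other way.
- **The cost scopes may not conflict.** In 3.2(d), the word for inclusion need not mean limitation. Only a restrictive reading makes the two sections different outcomes. This is a point of wording to reconcile, not a proven contradiction.

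The outcomes are also secondary, and sections 5 and 9.4 call the study a pilot.

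**Conclusion.** The point holds as a gap in pre-specification. For MacNew, ANCOVA on the day-0 score needs no new data and loses nothing of note against either unadjusted choice. The variance reduction is 9% to 49% against day-90 scores and 35% to 15% against change scores, for assumed correlations of 0.3 to 0.7.

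For cost, the rule would probably select a test that does not estimate the quantity named in the hypothesis. That conclusion rests on the likely skew implied by the 24% event rate; the degree of skew is assumed. It does not rest on power: for savings of about $800 to $1,600 from fewer or cheaper events, both tests succeed in at most about a third of simulated trials. A comparison of means gains the dollar scale, not reliable detection.

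Both outcomes are secondary, and the primary chi-square analysis is unaffected. The change is worth making because it is cheap.

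**What to change.** Add to section 9.6:

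> Day-90 MacNew score will be compared by ANCOVA with group and day-0 score. Cost per patient will be compared by the difference in arithmetic means with a bootstrap 95% confidence interval, whatever its distribution; Wilcoxon is supportive only.

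State one cost scope in both 3.2(d) and 9.5.2.1. One option is all services as the outcome, with cardiovascular services reported separately.

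This costs a few lines of text, with no new patients or visits. In six simulated settings at this sample size, the percentile bootstrap interval covered the true difference in 93.3% to 96.0% of trials, so the method is workable. The downside should be accepted openly: the cost interval will be wide (about ±$2,000 to $3,300 under the assumed costs), and power will be below Wilcoxon's in some scenarios, for example 48–60% against 57–68% when events fall from 48% to 30%.

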10. DATA COLLECTION AND QUALITY ASSURANCE

10.1. Data Collection Forms

The study case report form (CRF) is the primary data collection instrument for the study. All data requested on the CRF must be recorded. All missing data must be explained. If a space on the CRF is left blank because the procedure was not done or the question was not asked, write "N/D". If the item is not applicable to the individual case, write "N/A". All entries should be printed legibly in black ink. If any entry error has been made, to correct such an error, draw a single straight line through the incorrect entry and enter the correct data above it. All such changes must be initialed and dated. Do not erase or use "white-out" for errors. For clarification of illegible or uncertain entries, print the clarification above the item, then initial and date it. If the reason for the correction is not clear or needs additional explanation, neatly include the details to justify the correction.

The data collection tool for this study will be investigator-designed case report forms. The investigator will maintain complete and accurate study documentation in a separate file. Study documentation may include medical records, records detailing the progress of the study for each subject, signed informed consent forms, drug disposition records, correspondence with the study coordinator study monitor/sponsor, screening and consent information, severe adverse event reports, laboratory reports, subject diaries, data clarifications requested by the sponsor, and any other documentation deemed relevant and pertinent to the study and the study subjects. Subject data necessary for analysis and reporting will be entered into a validated database or data system in accordance. Clinical data management will be performed in accordance with applicable data management vendor standards and data cleaning procedures. The investigator is responsible for the procurement of data and for the quality of data recorded on the CRFs. The handling of data, including data quality assurance, will comply with regulatory guidelines (e.g., ICH GCP).

Source data is all information, original records of clinical findings, observations, or other activities in a clinical trial necessary for the reconstruction and evaluation of the trial. Source data are contained in source documents. Examples of these original documents, and data records include: hospital records, clinical and office charts, laboratory notes, memoranda, subjects' diaries or evaluation checklists, pharmacy dispensing records, recorded data from automated instruments, copies or transcriptions certified after verification as being accurate and complete, microfiches, photographic negatives, microfilm or magnetic media, x-rays, subject files, and records kept at the pharmacy, at the laboratories, and at medico-technical departments involved in the clinical trial.

The investigator will maintain records and essential documents related to the conduct of the study. These will include subject case histories and regulatory documents.

10.2. Data Management

All study data will be collected at Mayo Clinic with the Department of Cardiovascular Diseases as the primary coordinating and data management center.

RedCap will be used for clinical data management and randomization. These tools are institutionally supported and allow for rapid database development. The implementation of the software within a project includes training on the system's use, robust error checking, security considerations, and full audit trail. Balance, which is integrated into *RedCap*, allows for a variety of randomization and minimization algorithms.

Demographic and clinical data will be extracted from medical records including age and gender, vital signs, physical exam findings.

Data on clinical outcome/event reporting will include cardiac dysfunction and/or heart failure as well as major adverse cardiovascular events (including myocardial infarction, heart failure, arrhythmia, transient ischemic attack, and stroke).

The echocardiographic parameters that will be captured comprise systolic, diastolic LV and RV function including LVEF.

The angiographic parameters collected will include name of the coronary artery, degree of stenosis and location, number of diseased vessels and number of stents, PCI success and complications.

All individually identifiable patient records and data will be stored in a database under coded accession numbers. A password is required to gain access to this protected and privileged information. Only the approved and trained study staff will have access to the database. The sponsor will not have any access to the study data. For individuals providing data, e.g. core laboratory personnel, access will be limited to entering data only. All data are monitored regularly for entry and access, and a formal policy regarding protection of personal privacy is in place throughout Mayo Foundation. The key to identification of subjects will be maintained in a secure office environment under the direction of the investigators. The institutional commitment at Mayo Clinic to protect patients' (and study participants') privacy is a high priority.

10.3. Quality Assurance

10.3.1 Training

The study will be performed only by adequately trained personnel. This applies to the entire study team roaster. Only approved and trained study staff, experienced in trials such as these, will interact with the patients and manage the data forms and database. As part of the study data, the study team will collect data on ECG, echocardiography and other imaging tests which are ordered per routine care for the patients during their hospitalization.

10.3.2 Quality Control Committee

This study will not assemble a quality control committee.

10.3.3 Metrics

The same applies for all endpoint parameters. Computerized checks will be performed to ensure data integrity. These will be reviewed by a trained study staff for fidelity. Source document verification will be performed to ensure data fidelity as well. To ensure compliance with GCP and all applicable regulatory requirements, the sponsor or designee may conduct a quality assurance audit. Regulatory agencies may also conduct a regulatory inspection of this study. Such audits/inspections can occur at any time during or after completion of

the study. If an audit or inspection occurs, the investigator and institution agree to allow the auditor/inspector direct access to all relevant documents and to allocate his/her time and the time of his/her staff to the auditor/inspector to discuss findings and any relevant issues.

10.3.4 Protocol Deviations

Patients will be contacted by phone for the device testing several times during the first month. The next contact will occur by phone call at the end of the study (90 +/- 7 days after the randomization). If any deviation from the study protocol were noted, a record will be made on their study participation form and these patients will be flagged for review by the PI. The study team will then decide if a study deviation occurred that precludes continuation of study participation. If this were indeed the case, the patient will be notified. This individual will be removed from the study and will be replaced by another study participant.

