8.1.2 Enrollment, Baseline, and/or Randomization

All patients who consent to the study are considered to be enrolled as of the date of the consent.

Baseline Assessments- comprises a review for any cardiovascular diseases or risk factors, home medications. Additional data will be collected: type of AMI (location: anterior, inferior, posterior, lateral), troponin levels, baseline ECG, left ventricular function by echocardiography, Canadian Classification scale (CCS) of Angina(class I, II, III IV) .

Randomization- will be done once all inclusion and exclusion criteria are reviewed and the patient meets eligibility criteria. Patient and treating cardiologist will be informed which study group the patient was assigned. Patients assigned to group 1 will be discharged with standard medical therapy as indicated by AHA/ACC guidelines in post AMI patients treated with or without PCI. Patients in group 2 will be discharged with the standard medical treatment as indicated by AHA/ACC guidelines in post AMI patients treated with or without PCI plus they will receive the Smartheart 12 lead ECG home telemonitoring device for the period of 90 days (+/-7). Those patients will have short explanation on how the device works, how to adjust it on the chest and how to transmit the ECG.

A post-study questionnaire will be administered to patients randomized to the device group to collect feedback on their experiences with the device. Participation is voluntary, and responses will be anonymized to ensure confidentiality. The inclusion of this questionnaire will not impact the primary study objectives or patient safety.

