8.1 Schedule of Evaluations

Assessment	Screening, Enrollment, Randomization: pre-discharge (Day 0)	Week 1 (-3,+6 days)	Week 2 (-3,+6 days)	Week 4 (-3, +6 days)	Day 90 (Final) (+/- 7 days)
Informed Consent Form	X (R)				
Demographics	X				
Medical History	X				
Vital signs	X				
Physical Examination	X				
Current Medications	X				
Blood Chemistries	X				
Electrocardiogram	X				
Echocardiogram	X*				
Inclusion/Exclusion Criteria	X (R)				
Enrollment/ Randomization	X (R)				
Providing Device + Instructions	X (R)				
Quality of Life questionnaire (day 0)	X (R)				
Follow-up ECG and training call		X (R.S.)	X (R.S.)	X (R.S.Q)	
End of participation phone call, will include:					X (R)
• ED visits/Hospitalizations/MACE data /ccs					X (R)
• Current medications and if changed lately					X (R)
• Quality of Life questionnaire (day 90)					X (R)
Device collection (patient sending by mail)					X (R)

X Performed as standard of care (not specific for research)

X* If performed after the AMI event and pre-discharge

X (R) Research related only

X (R.S.) Research – Study group related only

X (R.S.Q) Research – Study group related only, depends on the need of further training beyond the first two tests.

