13. COMMITTEES

This study will not convene any particular committee such as a Steering Committee or an Executive Committee, a Publication Committee, or an Adjudication Committee.

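### Section 10.3.4 lets a study team that can know the allocation remove and replace randomized patients, and nothing keeps them in the primary analysis

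*Combined protocol and SAP*

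**What the plan says.** Section 10.3.4 (Protocol Deviations) has any deviation recorded and flagged for review by the principal investigator. Then: "The study team will then decide if a study deviation occurred that precludes continuation of study participation". If the answer is yes, the patient is told, and "This individual will be removed from the study and will be replaced by another study participant". The section does not list which deviations qualify, sets no time limit and does not blind the decision.

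The same section describes how patients are contacted: "Patients will be contacted by phone for the device testing several times during the first month", with a final call at day 90. The schedule in Section 8.1 labels the week 1, 2 and 4 calls "Study group related only". The day-90 call is made in both arms and also collects ED visits, hospitalizations and MACE.

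On allocation, Section 8.1.2 says: "Patient and treating cardiologist will be informed which study group the patient was assigned". Section 13 rules out "a Publication Committee, or an Adjudication Committee".

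Section 9.6 defines the primary analysis as "a comparison of the rates of the primary combined endpoint between group 1 and 2 via Chi square test". It does not say which patients are included.

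**The concern.** The people removed under this rule have already been randomized. Taking some out afterwards and enrolling others in their place means that the compared groups are defined partly by a post-randomization judgement. Three features make this more than a formality.

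- **Unequal detection.** Device patients have up to three extra scheduled contacts in the first month at which a deviation can be noticed. Controls have no scheduled study contact before day 90.
- **Knowledge at the time of decision.** Study staff give out the device and make the device-only calls, and no blinding of them is described. It is therefore a strong inference, though not a stated fact, that they know the arm. A control deviation noted at the day-90 call may be judged when that patient's outcome is already known.
- **No safeguard downstream.** No intention-to-treat statement, no missing-data rule and no provision for following removed patients appears in the text supplied. Section 11 allows continued use of data already collected, but only after a patient revokes authorization for health information. Appendix A, Table 3 has columns for adherence and reason for withdrawal; that is reporting and does not return anyone to the comparison.

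At stake is the validity of the primary test. The sample size re-estimation in Section 9.4 is exposed too, because it uses the device-arm rate alone.

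**Working it through.** **Inputs from the documents.** Control event rate 48%, relative reduction 37.5%, 120 per arm, alpha 0.05 and beta below 0.2 (Section 9.2); 1:1 allocation (9.3); chi-square test (9.6). Sidedness is not stated, so two-sided is assumed.

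**Step 1: the plan's own power.** The device rate is 0.48 × (1 − 0.375) = 0.30. Using the normal approximation to the chi-square test with pooled variance under the null:

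- mean rate 0.39; null SE = √(2 × 0.39 × 0.61 / 120) = 0.0630
- alternative SE = √((0.48 × 0.52 + 0.30 × 0.70) / 120) = 0.0619
- power = Φ((0.18 − 1.96 × 0.0630) / 0.0619) = 82.0%

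The stated beta below 0.2 is reproduced.

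**Step 2: effect of removal when the device does nothing.** Assume that a share f of device patients is removed, that their risk is RR times the risk of those kept, that replacements face the same rule, and that no control is removed. The documents give neither f nor RR. The rate among analysed device patients is

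kept rate = 0.48 / (1 − f + f × RR).

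Example: f = 0.20 and RR = 1.5 give 0.48 / 1.10 = 0.4364. The rejection probability of the Step 1 test at 0.48 versus 0.4364, 120 per arm, both tails, is 10.4%.

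| RR | f | Analysed device rate | Implied rate in those removed | Type I error |
|---|---|---|---|---|
| 1.5 | 5% | 46.8% | 70.2% | 5.4% |
| 1.5 | 10% | 45.7% | 68.6% | 6.4% |
| 1.5 | 20% | 43.6% | 65.5% | 10.4% |
| 2 | 5% | 45.7% | 91.4% | 6.4% |
| 2 | 10% | 43.6% | 87.3% | 10.4% |
| 2 | 20% | 40.0% | 80.0% | 23.8% |
| 1 | any | 48.0% | 48.0% | 5.0% |
| 0.67 | 10% | 49.6% | 33.3% | 5.7% |
| 0.67 | 20% | 51.4% | 34.4% | 8.2% |

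At RR above 1 the bias favours the device; at RR below 1 it goes against it.

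**Step 3: the re-estimation.** The Section 9.4 examples (17.5% gives 181 per group, 10% gives 62) reproduce with n = [1.96√(2p̄(1 − p̄)) + 0.842√(p₁(1 − p₁) + p₂(1 − p₂))]² / (p₁ − p₂)² at 80% power if the control rate is 30%. Section 9.4 does not state that rate; it is inferred from the fit. If the true device-arm rate were 17.5% and removed patients had RR = 1.5:

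- 10% removed: 0.175 / 1.05 = 16.7%, giving 157 per group
- 20% removed: 0.175 / 1.10 = 15.9%, giving 139 per group

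Either falls short of 181, so the trial would be undersized for the rate that actually applies.

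**Step 4: what keeping everyone costs.** If a share u of device patients gets no benefit, the device rate is 0.30(1 − u) + 0.48u. With u = 10% it is 31.8%: power at 120 per arm is 72.9%, and 80% power needs 143 per arm. With u = 20% it is 33.6%: power is 62.3%, and 80% needs 182 per arm. Both shares are assumptions.

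**The case against.** The strongest reply is that Section 10.3.4 ends participation and does not say that the data are discarded. Section 9.6 compares groups that Section 5 defines by randomization, and the adverse event paragraph in Section 5 mentions retrospective follow-up of events, so outcomes might still be captured. It is true that exclusion is implied and not stated. But replacement has little purpose if the first patient still counts, the enrolment table in Appendix A subtracts withdrawn patients from the running total, and the retrospective follow-up sets no analysis population.

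Second, the rule asks whether continuation is precluded, and at day 90 little continuation remains, so the control-arm route may matter less than the first-month one. That is a fair limit on its weight. It does not close the route, because the section names the day-90 call just before it gives the rule.

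Third, the size may be small. This stands: at 5% removed the type I error is only 5.4% at a risk ratio of 1.5 and 6.4% at 2, and the largest figures need removed patients to have event rates of 80% or more. However, the plan sets no limit on removals.

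Fourth, the study calls itself a pilot. It nevertheless runs a powered hypothesis test at alpha 0.05.

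Finally, the absence of an adjudication committee is a minor point, since the documents do not give such a body the task of ruling on deviations.

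**Conclusion.** The rule is wrong as written and must be changed. Followed literally, it can replace a randomized comparison with one shaped by undefined decisions that are probably made with the arm known.

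The documents fix neither the direction nor the size of the bias. With device-arm removals only and no true effect, type I error stays at 5.0% if removal is unrelated to risk. It is about 5.4% to 10.4% for 5% to 20% removed at a risk ratio of 1.5, and reaches 23.8% at 20% removed and a risk ratio of 2. Equal removal of comparable patients in both arms would cause no such bias, but the device-only calls make that unlikely. The re-estimation result rests on the further inference of a 30% control rate and is secondary.

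**What to change.** Amend three sections.

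- **10.3.4:** record and report deviations, but do not make them grounds for removal from follow-up or analysis. Delete replacement: no newly enrolled patient substitutes for a randomized one in the analysis.
- **9.6:** state that every randomized patient is followed to day 90 for the primary endpoint, whether or not the device is used, and is included in the primary chi-square test in the assigned group. Extend to withdrawal of consent the retention of earlier data that Section 11 now gives only for revoked authorization. A per-protocol analysis may be added as a sensitivity analysis.
- **9.4:** apply the same population to the re-estimation.

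The direct cost is protocol wording. The day-90 call already exists, and the change itself requires no added enrolment. The cost to acknowledge is power: if the 37.5% reduction does not already allow for device non-use, the dilution in Step 4 applies, and holding 80% power would mean more patients. That diluted effect is the as-randomized effect the trial sets out to measure.
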